In our department in Orléans, France, 47% of the admitted patients have at least one day with an IAC. Ninety-four per cent (94%) of patients receiving continuous iv vasopressor therapy and 80% of patients placed under invasive mechanical ventilation also receive an IAC during their ICU stay. Large-scale multicentre data regarding the frequency of IAC use in French ICUs are lacking. However, our local practice seems quite close to that of other ICUs in France: In a recent multicentre observational study from our group that focused on volume expansion practice in patients with circulatory failure in 19 French ICUs (including most of the 11 participating centres anticipated for the present project), we observed that 53% of patients were already carrying an IAC at the time they received their first fluid bolus in the ICU. This proportion increased parallel to the number of fluid boluses received to reach 100% in patients receiving more than seven fluid boluses. We also observed that, on average, more than 85% of patients who were receiving continuous iv vasopressor therapy at the time they were administered a fluid bolus, were carrying an IAC at the same time.(3)

The reasons for this widespread use of IAC are that it allows continuous measurements of blood pressure, a key physiological variable that drives organ perfusion, and facilitates blood sampling for laboratory testing while avoiding several vascular punctures.(1,4,5) Therefore, despite the lack of high-level evidence of the benefits it could bring to ICU patients, the IAC insertion is commonly recommended to manage patients with septic shock or other kinds of shock.(6,7)

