- Number of Adverse Events of special interest (Ischemia and/or necrosis of finger(s) or toe(s), documented bowel ischemia, occurrence or worsening of acute renal failure with need of renal replacement therapy, need of tracheal intubation in a patient previously not intubated, Cardiac arrest, nerve injury of upper limb(s), skin lesions at cuff location or at IAC insertion site, arterial thrombosis, hematoma, arterial pseudo aneurysm, haemorrhage at IAC insertion site either during IAC placement or later)
- Incremental Cost-Effectiveness Ratio (ICER): «Cost/Life day gained at 28 days», from the health system viewpoint, between the non invasive strategy and the recommended invasive strategy: $(\text{Costs}_{\text{NIBP}} - \text{Costs}_{\text{IAC}}) / (\text{Life expectancy at D28}_{\text{NIBP}} - \text{Life expectancy at D28}_{\text{IAC}})$
- Budget impact analysis of the generalization of the non-invasive strategy (in case of demonstrated non inferiority) in France from the viewpoint of the French health system on a 5 years' time frame
- Patient-reported pain and discomfort related to the device used for BP monitoring will be assessed using numerical scales in both groups, once a day as soon as the patients are awakened and capable of correctly evaluating their pain and discomfort (cf. APPENDIX 1)

3. Interventions

Once included, the patient will be randomly assigned, for the 28 following days, to one of the following strategies:

a) **“usual care”**: An IAC will be inserted as soon as possible (within the first four hours after randomization)

and will be maintained except in case of IAC futility (as defined below), suspected or proven IAC related infection or thrombosis (at discretion of attending physician) until day 28 or ICU discharge (whichever comes first). After day 28, clinicians may choose to maintain or to remove IAC.

During the intervention period, in case of removal for accidental or other reasons than futility (i.e. IAC infection, IAC dysfunction, unavailability to draw blood), another IAC should be inserted during the next four hours (insertion site at the discretion of the attending physician).

In case of IAC removal for other futility criteria than decision of palliative care, an IAC will be inserted within the four hours of new onset of circulatory failure as defined below:

- Presence of
 - Persisting hypotension (systolic blood pressure less than 90 mmHg or mean arterial blood pressure less than 65 mmHg) for more than 4 hours

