 - OR requirement of continuous iv vasopressor treatment (i.e. noradrenaline tartrate at a dose $\geq 0,2 \mu\text{g}/\text{kg}/\text{min}$ or any dose of epinephrine) for more than 4 hours
- AND at least one of the following signs of hypoperfusion: alteration of mental status; skin mottling; oliguria defined as a urine output $< 0.5 \text{ mL/kg body weight}$ for at least one hour; arterial lactate $> 2 \text{ mmol/L}$; peripheral venous lactate $> 3.2 \text{ mmol/L}$; $\text{ScvO}_2 < 70\%$

b) **“non-invasive care”:** No IAC insertion will be allowed during the first 28 days, excepted if predefined safety criteria (indicating absolute need of IAC insertion) are reached (see below): IAC will be inserted within the 4 hours of presence of safety criteria and patient will be managed as if he/she were part of usual care group until day 28 or ICU discharge. Arterial blood draw is allowed via direct arterial puncture as frequently as indicated.

Criteria of IAC futility (one or more criteria defined futility) allowing IAC removal at physician’s discretion:

- The patient no longer needs significant vasopressor therapy (i.e. no longer needs norepinephrine tartrate at a dose $\geq 0,2 \mu\text{g}/\text{kg}/\text{min}$ or any dose of epinephrine) for more than 4 hours, and exhibits no sign of hypoperfusion (i.e., neither alteration of mental status, skin mottling, oliguria defined as a urine output $< 0.5 \text{ ml/kg body weight}$ for at least one hour, arterial lactate $> 2 \text{ mmol/L}$, peripheral venous lactate $> 3.2 \text{ mmol/L}$ or $\text{ScvO}_2 < 70\%$)
- Medical decision of palliative care

Safety criteria for IAC insertion for patients initially randomized in the “no-IAC” group:

As undisputable criteria are lacking in the medical literature, criteria were consensually determined (Delphi method) after collecting the opinion of the anticipated investigators (senior ICU physicians) in each centre. After two turns of notation, the following criteria were retained (since the median of notation fell between 7 and 9 on a 9-point scale; extending from score 1 [“do not agree at all”] to score 9 [fully agree]) with low

- Although the pulse oximetry monitor was working well at inclusion, it can no longer display any reliable SpO₂ value
- Despite NIBP readings were available at inclusion, NIBP now consistently fails to display any reliable BP value

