4.3. Inclusion and non-inclusion criteria

Inclusion criteria

- Age \geq 18 years the day of inclusion
- Existence of an acute circulatory failure defined by the presence of the following items 1 and 2:
 - 1) Persisting hypotension (systolic blood pressure less than 90 mmHg or mean arterial blood pressure less than 65 mmHg) for more than 15 min at ICU admission or within the following

24 hours, **OR** requirement of continuous iv vasopressor treatment (i.e. any dose of norepinephrine / epinephrine)

- 2) Presence at least one of the following signs of hypoperfusion: alteration of mental status; skin mottling; oliguria defined as a urine output < 0.5 mL/kg body weight for at least one hour; arterial lactate > 2 mmol/L; peripheral venous lactate > 3.2 mmol/L; ScvO₂ <70%
- Free express oral and informed consent of the patient or a proxy in case of impossibility for the patient to consent; emergency inclusion possible when legal representatives and patient's family are not available
- French health insurance holder

Non-inclusion criteria

- Acute circulatory failure, as defined by items 1 and 2 in inclusion criteria list (cf. supra) present for more than 24 hours
- NIBP device fails to display a BP value, or cuff placement impossible
- Patient for whom an ECMO therapy (either veno-arterial or venous-venous) is already in place or is to be initiated within the next 6 hours
- Patient treated with vasopressor doses of more than 2.5 µg/kg/min of *norepinephrine tartrate* plus epinephrine for at least 2 hours (i.e., for instance, more than 8 mg of *norepinephrine tartrate* in 50 mL at the rate of 66 mL/hour for a patient weighing 70 kg) (*please note that in fact this dosage corresponds to 1.25 µg/kg/min of norepinephrine base*)
- Severe traumatic brain injury (i.e., traumatic brain injury with a Glasgow coma scale score of less than 9 before sedation)
- Patient previously included in the trial
- Body mass index (BMI) above 40 kg/m² (33,35,65)
- Pregnancy
- Brain death
- Moribund patient
- Patient known, at time of inclusion, as being under guardianship, tutorship or curatorship

[figure not shown]
N.B.: Note that a patient already carrying an indwelling arterial catheter can still be randomized in the study provided that all the above criteria are respected. If randomised in the “noninvasive group”, the catheter should be removed within one hour following randomisation.

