Deferring arterial catheterization in critically ill patients with shock – EVERDAC trial

STATISTICAL ANALYSIS PLAN — December 2024

The initial Statistical Analysis Plan established before launching the study and published in BMJ Open in 2021 ([name] et al. BMJ Open 2021;11:e044719. doi:10.1136/bmjopen-2020-044719) was amended after the blind review of the data in December 2024.

Level of statistical significance

Statistical significance threshold will be set at 5%, and 95% two-sided confidence intervals (95%CI) will be calculated for all estimates.

Analyzed population

All randomized patients, except for patients who secondarily object to the use of their data or protected under guardianship, will be included in the analysis. No interim analysis will be performed.

Two per-protocol populations were defined during the blind review:

- In the first per-protocol population, we will exclude patients wrongly included, and patients from the noninvasive group in whom the arterial catheter previously inserted was not removed after the randomization. In the invasive group, we will exclude the patients who either did not undergo an attempt at arterial catheter insertion or had the arterial catheter insertion more than 24h after randomization.
- In the second per-protocol population, we will exclude patients from the invasive group who did not receive an arterial catheter within 24h after randomization, regardless of the reason (unsuccessful arterial catheter insertion, no attempt of arterial catheter insertion or insertion occurring more than 24h after randomization). The per-protocol population in the noninvasive group will remain unchanged for the second per-protocol analysis.

Description of baseline characteristics

All data recorded at baseline will be summarized by treatment group using means and standard deviation for normally distributed quantitative variables, median and interquartile range for other quantitative variables, and counts and percentages for qualitative variables. No statistical test will be used.

Primary outcome

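### Both per-protocol sets drop invasive-arm patients who die before any catheter attempt, while noninvasive patients without a prior catheter who die equally early stay in

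*SAP*

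**What the plan says.** The SAP (Analyzed population) defines two per-protocol sets, fixed at the blind review.

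- **Invasive arm, first set:** "we will exclude the patients who either did not undergo an attempt at arterial catheter insertion", or whose insertion came after 24 h.
- **Invasive arm, second set:** it drops "patients from the invasive group who did not receive an arterial catheter within 24h after randomization, regardless of the reason". The listed reasons include a failed insertion and no attempt.
- **Noninvasive arm:** apart from patients wrongly included (a rule not limited to one arm), it drops only "patients from the noninvasive group in whom the arterial catheter previously inserted was not removed after the randomization". For the second set: "The per-protocol population in the noninvasive group will remain unchanged for the second per-protocol analysis".

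No rule mentions death.

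The protocol supplies the timing. In usual care (section 3): "An IAC will be inserted as soon as possible (within the first four hours after randomization". Section 4.3 adds that "a patient already carrying an indwelling arterial catheter can still be randomized in the study" and that such a catheter is due for removal within one hour if the patient is allocated to the noninvasive arm. Section 6.2 plans per-protocol beside intention-to-treat because this is a non-inferiority trial.

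**The concern.** Day-28 death is the primary outcome, and under these rules an early death can itself be the reason for exclusion. A control patient who dies two hours after randomisation, before anyone has attempted a catheter, followed the protocol for as long as they lived. Removing that patient removes an event, not a deviation. A noninvasive patient without a prior catheter who dies at the same hour is retained.

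The match between the arms is only partial. Read literally, the removal rule also drops a noninvasive patient who arrived with a catheter and died before it came out, but that covers carriers only. A control patient who dies after a failed attempt leaves the second set but not the first.

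Readers of a non-inferiority trial use the per-protocol result to check the all-randomised one. If the two differ partly because of this rule, the difference cannot be interpreted unless the exclusions are set out by reason.

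**Working it through.** **Inputs.** Protocol 6.1: mortality 25% control and 22.5% experimental, margin 5 points, power 80%, alpha 5%, 1010 patients. Protocol 4: 1:1 allocation, so 505 per arm. Protocol 6.2: upper limit of the two-sided 95% CI against the margin. The documents give no rate of early death, of carriers at randomisation, or of uncatheterised controls. Those rates are assumptions below.

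**Plan's own figure.** n per arm = (1.960 + 0.842)² × (0.225×0.775 + 0.25×0.75) / 0.075² = 504.9, so 505 per arm and 1010 in total. The stated size is reproduced at one-sided 2.5%.

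**Formula.** P(declare NI) = Φ[(0.05 − (pE − pC))/SE − 1.96], with unpooled SE and 505 per arm less those excluded. At the design rates this is 80.0%.

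**Step 1: early control deaths alone.** If a share d of controls die before an attempt, pC = (0.25 − d)/(1 − d). A fall in pC moves the difference (noninvasive minus invasive) upwards, against non-inferiority.

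| d | patients | pC | fall in pC | P(NI) at pE = 22.5% |
|---|---|---|---|---|
| 0.2% | about 1 | 24.85% | 0.15 points | 78.4% |
| 0.5% | about 3 | 24.62% | 0.38 points | 75.9% |
| 1% | about 5 | 24.24% | 0.76 points | 71.4% |

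At a true 5-point harm (30% against 25%) and d = 1%, the chance of falsely declaring non-inferiority falls from 2.5% to 1.3%. Alone, the rule is conservative.

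**Step 2: the carrier mirror, d = 1%.** Let f be the ratio of noninvasive carriers dropped for early death to controls dropped for early death; pE = (0.225 − fd)/(1 − fd). Assume control carriers count as catheterised, so that only control non-carriers can die before an attempt. For the carrier share, take the protocol's background figure from another cohort, "53% of patients were already carrying an IAC at the time they received their first fluid bolus in the ICU". It was not measured at randomisation, so it is only a guide.

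- Equal early risk and equal windows: f = 0.53/0.47 = 1.13; pE = 21.61%; difference 21.61 − 24.24 = −2.63 points. Net shift from −2.50: −0.13 points, P(NI) 81.8%.
- Scaled for the one-hour removal window against four hours for insertion: f = 1.13/4 = 0.28; pE = 22.28%; difference −1.96 points. Net shift +0.54 points, P(NI) 74.2%.

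The sign depends on the assumed f.

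**Step 3: low-risk controls, d = 1%, mirror left out.** Some controls with no or late insertion may simply have improved. If a share x with 10% mortality is also excluded, pC = (0.25 − 0.01 − 0.10x)/(1 − 0.01 − x):

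- x = 2%: 24.54%
- x = 5%: 25.00%
- x = 10%: 25.84%

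At x = 5% the two exclusions cancel; beyond that, the rule favours non-inferiority.

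**Step 4: effect of keeping the early deaths.** With x = 5%, pC = (0.25 − 0.005)/0.95 = 25.79%. At a true 30% against 25%, false non-inferiority is 4.6%. Under the present rule, with d = 1% and x = 5%, it is 2.5%.

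**The case against.** The strongest reply concerns weight. The primary analysis uses all randomised patients. Neither document sizes the trial on a per-protocol set or makes one a condition for concluding non-inferiority, so the P(NI) figures describe a supporting analysis. This stands.

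The rates may also be very small. Catheters are to be placed as soon as possible, moribund and brain-dead patients are not eligible, and wrongly included patients are removed. With the 53% carrier figure, d = 2% would mean 0.02/0.47 = 4.3% of non-carrier controls dying before an attempt, which is hard to credit. For that reason the table stops at 1%. This stands too, but it reduces the size of the asymmetry without removing it.

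A third reply is that redefining the sets now would be a change towards non-inferiority after the blind review. Protocol 6.2 requires modifications before unblinding, and the SAP's summary of changes records some choices made during analysis. This stands and shapes the fix.

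A reader might infer that the rule helps the noninvasive strategy look non-inferior, or that it reliably works against it. The documents support neither, because they give no counts by reason.

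A reader might also infer that noninvasive patients catheterised outside the safety criteria go unexamined, since protocol section 3 says "No IAC insertion will be allowed during the first 28 days, excepted if predefined safety criteria" are met and neither set removes such patients. That goes too far. The SAP plans counts by arm of patients reaching the vasopressor limit, and it reports that noninvasive insertions after reaching it had already been observed. Only the remaining criteria lack a split, and this is a secondary matter.

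**Conclusion.** The asymmetry is a plain reading of the SAP and should be addressed. Both sets exclude invasive-arm patients because they died before an attempt, including deaths that involve no deviation, and the noninvasive arm has only a partial counterpart. The effect is confined to the per-protocol analyses.

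Its size rests on assumed rates. The invasive-arm exclusion alone shifts the difference by 0.15 to 0.76 points against non-inferiority for d from 0.2% to 1%. At 1%, the carrier mirror brings the net shift to between about +0.54 and −0.13 points, and low-risk uncatheterised controls can cancel or reverse it. The net direction is therefore unknown. Confidence is high on the reading and low on the magnitude.

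**What to change.** 1. **Add a per-protocol analysis** that does not exclude patients in either arm who died before their insertion or removal window closed without a prior deviation. State the windows the analysis uses: the protocol allows four hours for insertion while the SAP tolerates 24 h, and the SAP's removal rule has no time limit while protocol 4.3 gives one hour. If the data have already been unblinded, label this analysis post hoc and keep the two SAP sets beside it.
2. **For each per-protocol set, tabulate exclusions by arm and reason, with day-28 deaths in each.**

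Optionally, report noninvasive-arm insertions under the safety criteria other than the vasopressor limit. This may need record review, and one criterion (high-risk surgery) is left to the physician's discretion.

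**Cost.** Item 1 is a sentence and one further analysis. Protocol 2.3 uses the date of death and no hour is listed, so the hour may have to come from source records for a few patients. Item 2 is one table.

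**Downside.** Item 1 on its own moves the per-protocol estimate towards non-inferiority and can remove an accidental offset (step 4: 4.6% against 2.5%). It should be read only together with item 2.
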